5.8.2 Individual subject

Once the liver has been transplanted there is no further trial intervention so there are no criteria for withdrawing patient from study

5.8.3 Trial

The trial will end if:

- 30 DBD and 30 DCD livers have been transplanted
- Evidence of residual thrombolytic activity in the livers post transplant. However, it is common in DCD liver transplantation for the patient to become coagulopathic post implant with evidence of fibrinolysis
- ≥ 5 cases of anastomotic or non-anastomotic strictures within six months of transplant

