2.9 Trial summary

Livers from donors donating after circulatory arrest (DCD donors) are associated with a high incidence of bile duct strictures after transplantation. This remains the case for liver subject to *ex situ* normothermic perfusion (NESLiP) prior to transplantation, with a rate of around 20% for anastomotic and non-anastomotic strictures. Livers from brain dead donors have a lower incidence of strictures after NESLiP at around is 8%, but they are equally disabling. Recent work in Cambridge has shown that DCD livers during NESLiP develop infarcts in the stromal walls of bile ducts in association with fibrin plugs in the peri-biliary blood supply, suggesting that these fibrin plugs may be the cause of the stromal infarcts, and by extrapolation the bile duct strictures. Subsequent work has shown that by using a similar thrombolytic protocol with tissue plasminogen activator (TPA, alteplase) to that used for clearing clots from the coronary circulation in patients having heart attacks results in no visible fibrin plugs and no bile duct necrosis.

In this study livers will undergo NESLiP and receive an infusion of TPA using a standard thrombolytic regimen for the first 60 minutes of perfusion, with a minimum perfusion time of 2 hours. Alteplase has a half-life of 5 minutes *in vivo* and a 1 hour perfusion will mean there will be at least 60 minutes between the end of the TPA infusion and removing the liver from the machine. Not all DCD donor livers will be viable on testing during NESLiP, but experience suggests that two thirds will meet the viability criteria and be transplanted. It is unlikely that there will be any active TPA in the circuit at the point of removal from the machine. Recipients will then undergo standard follow up with no further research intervention.

This study is a pilot study of 30 DCD and 30 DBD transplants to assess the safety of thrombolysis during *ex situ* perfusion, and to give an idea of its effects on the subsequent outcome of the implanted liver with particular reference to early function and bile duct strictures. The results will be compared with recipients randomised to receive FFP and no TPA. If the study suggests that the intervention is safe and efficacious the protocol will be used in a larger scale multicentre study.

3 Study Flow Chart

Donor liver placed on OrganOx *metra* machine

[figure not shown]

Figure 1: Flow chart for NESLiP assessment of donor livers

4 Background

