5.4 Sample size determination

Previous experience with back-to-base perfusion of DCD livers has been associated with a 20% incidence of anastomotic strictures and a 20% incidence of non-anastomotic bile duct strictures (unreported Cambridge data). In a cohort of 20 patients receiving a DCD liver treated by NESLiP it is likely that one will die, five will undergo retransplantation and four will develop non-anastomotic strictures. Similarly, the incidence of non-anastomotic strictures in DBD livers undergoing NESLiP in Cambridge is 8%, with a further 15% suffering anastomotic strictures.

A sample size of 30 DBD and 30 DCD should allow us to evaluate the safety of this therapy. It may also help determine whether the thrombolytic regimen increases the proportion of perfused livers that get transplanted and abolishes non-anastomotic strictures, and therefore whether it is worth proceeding to a formal randomised study and how to power that study

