11.3 Expected Serious Adverse Events

Liver transplantation is a life-saving procedure but is associated with serious life-threatening complications. It is expected that many of these will be encountered during the study and which we do not propose to report as AEs or SUSARs to the REC/Sponsors.

- Peri-operative death (within 48h) ~ 1 to 2%
- Death from graft failure or sepsis or other complication in the first year: 5%
- Primary non function: 4% for DCD livers; 1% for DBD livers
- Early allograft dysfunction (Olthoff criteria): 40% DCD, 25% DBD.
- Hepatic artery thrombosis: 4-15%, depending whether anomalous arterial supply required reconstruction or not
- Post reperfusion syndrome: 30%
- Biliary anastomotic breakdown 5%
- Post-operative haemorrhage requiring reoperation: 10%
- Acute rejection: 20%
- Acute kidney injury (Rifle definition): 50% DCD, 35% DBD.
- Chest complications: sepsis; effusion; paralysed right hemidiaphragm: common
- Ascites: universal if pre-existing ascites, common if not pre-existing.

- Complication associated with operative techniques in particular, or surgery in general (e.g. adhesions, adhesive obstruction, wound infection, wound hernia, wound dehiscence)
- Line sepsis
- Biliary anastomotic stricture: 20% DCD, 15% DBD
- Non-anastomotic strictures: 20% DCD, 8% DBD
- Retransplantation in first year: 17% DCD, 11% DBD.

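### The limit of five strictures that ends the trial lies well below the number the protocol's own background rates predict, so it cannot separate harm from background

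*Protocol*

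**What the plan says.** Section 5.8.3 lists three events that end the trial. One is completion, when "30 DBD and 30 DCD livers have been transplanted". Another is ≥ "5 cases of anastomotic or non-anastomotic strictures within six months of transplant". The second is an absolute count. It does not say out of how many recipients, whether DCD and DBD recipients are pooled, or whether recipients randomised to FFP without TPA are included. No section explains the choice of five.

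The protocol states elsewhere what it expects without TPA. For DCD livers, section 5.4 reports "a 20% incidence of anastomotic strictures and a 20% incidence of non-anastomotic bile duct strictures". For DBD livers it says that "the incidence of non-anastomotic strictures in DBD livers undergoing NESLiP in Cambridge is 8%, with a further 15% suffering anastomotic strictures". Section 11.3 repeats these figures among the expected complications that will not be reported as adverse events: "Biliary anastomotic stricture: 20% DCD, 15% DBD" and "Non-anastomotic strictures: 20% DCD, 8% DBD". Section 2.9 can be read lower. It describes DCD livers "with a rate of around 20% for anastomotic and non-anastomotic strictures", which could mean both types together, and gives about 8% for DBD livers.

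**The concern.** The same events are routine background in section 11.3 and grounds for ending the trial in section 5.8.3. A stopping limit is useful only if it is unlikely to be reached when the treatment is harmless and likely to be reached when it harms. A limit that background alone will reach carries no information about TPA.

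Two things are at stake. Section 4.9.2 wants stricture data to power a larger study, and an early stop would cut those data short. A stop would also look like a safety signal when it reflected the usual rate. Section 2.6 lists no committee and section 10.7 rules out external supervision, so no independent body is named to put the count in context.

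**Working it through.** **Inputs.** 30 DCD and 30 DBD transplants (5.8.3). Anastomotic rates 20% DCD and 15% DBD; non-anastomotic rates 20% DCD and 8% DBD (5.4, 11.3). Lowest reading 20% DCD and 8% DBD for all strictures (2.9). One transplanted liver in six is a control (section 7), so about 50 of 60 recipients (25 DCD, 25 DBD) receive TPA. Recruitment within a year or sooner (5.5).

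**The protocol's own projection.** Section 5.4 expects four non-anastomotic strictures in 20 DCD recipients: 20 × 0.20 = 4. This reproduces. The protocol gives no stopping probabilities for the limit itself.

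**Rate of any stricture per recipient, TPA inert.**
- The two types never coincide: DCD 0.20 + 0.20 = 0.40; DBD 0.15 + 0.08 = 0.23.
- The two types are independent: DCD 1 − 0.80 × 0.80 = 0.36; DBD 1 − 0.85 × 0.92 = 0.218.

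**Non-anastomotic strictures abolished, anastomotic unchanged:** DCD 0.20; DBD 0.15.

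**Formulas.** Expected cases = 30 × p(DCD) + 30 × p(DBD). P(≥5) is the upper tail of the sum of Binomial(30, p(DCD)) and Binomial(30, p(DBD)), computed exactly. For TPA-treated recipients only, 25 replaces 30.

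| Scenario | DCD / DBD | Expected in 60 | P(≥5), all 60 | P(≥5), 50 treated |
|---|---|---|---|---|
| No effect, additive | 40% / 23% | 18.9 | >0.999 | >0.999 |
| No effect, independent | 36% / 21.8% | 17.3 | >0.999 | >0.999 |
| Non-anastomotic abolished | 20% / 15% | 10.5 | 0.986 | 0.95 |
| No effect, lowest reading | 20% / 8% | 8.4 | 0.94 | 0.85 |

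Conversely, P(≥5) in 60 falls to 10% only at an overall stricture rate of 4.1%. The independent rates average (36% + 21.8%) / 2 = 28.9%.

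**Six-month horizon.** The stated rates have none. If half of the strictures arise by six months (assumption), for all 60:
- No effect, independent (18% / 10.9%): 8.7 expected, P = 0.95. Additive (20% / 11.5%): 9.45 expected, P = 0.97.
- Non-anastomotic abolished as well (10% / 7.5%): 5.25 expected, P = 0.61.
- Lowest reading (10% / 4%): 4.2 expected, P = 0.41.

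**Timing.** The figures above apply at the end of six-month follow-up. Simulation with even accrual gives the probability that the fifth case comes before the last transplant. The ranges run from all strictures recognised at month six to onset uniform over months 0 to 6 (both assumptions).

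| Scenario | 12-month accrual | 6-month accrual |
|---|---|---|
| No effect, independent | 0.95 to >0.99 | 0 to 0.95 |
| Non-anastomotic abolished | 0.59 to 0.91 | 0 to 0.60 |
| No effect, lowest reading | 0.38 to 0.77 | 0 to 0.40 |

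**The case against.** The strongest objection is about timing. A reader might infer that the rule will almost certainly halt the trial even if TPA works as hoped. The documents do not support that. Section 5.8.3 also ends the trial at 30 DBD and 30 DCD transplants, and a fifth stricture after the last transplant cuts no enrolment. Section 5.5 allows recruitment faster than a year. If non-anastomotic strictures are abolished, the chance of a stop before the last transplant is 0.59 to 0.91 at best and can be zero with fast accrual and late recognition. This objection stands.

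The rates are also uncertain. They have no six-month horizon, section 9.5.4 records MRCP only where one was done, and section 2.9 can be read lower. This weakens the claim under benefit. It does not rescue the rule: even the most favourable of the no-effect cases tabulated for 60 recipients reaches the limit about four times in ten.

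Two further readings are tempting. One is that controls count towards the five. Section 5.8.3 does not say, so the fault is ambiguity. The other is that five was carried over from a smaller design. The amendment log does not mention the threshold, and 20 DCD recipients at these rates would give 7.2 to 8 cases (20 × 0.36 to 20 × 0.40), so five would not fit that cohort either.

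Finally, strictures are a secondary endpoint. The primary ones in section 5.6.1, blood loss and feasibility, are known at surgery for each recipient transplanted. A low precautionary limit can be a legitimate choice in a novel pilot, but the protocol gives no such rationale, and a limit that background alone reaches does not serve as a precaution.

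**Conclusion.** The concern holds as a conflict between the stopping limit and the protocol's own rates. On the rates in 5.4 and 11.3, reaching five cases by the end of follow-up is near certain if TPA is inert (above 0.999; about 0.95 if only half arise by six months). It is likely to very likely if non-anastomotic strictures are abolished (0.986 counting all recipients, 0.95 counting treated recipients only, 0.61 counting all recipients with half arising by six months). The last three figures assume no effect of TPA on anastomotic strictures. The rule therefore cannot tell harm, no effect and benefit apart. Early closure of enrolment is a separate and less certain consequence: probable under no effect with a year's accrual on those rates, and open under benefit or faster accrual. Because the rule is written as binding, it should be corrected before it is applied.

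**What to change.** Reconcile section 5.8.3 with the rates in 5.4 and 11.3 by amendment:
- Express the limit relative to the expected rates in 11.3 or to the concurrent controls, separately for DCD and DBD. With one control in six, the control comparison will be imprecise.
- State who counts (TPA-treated or all recipients), which stricture type counts, the denominator and the look times.
- Give the background rates a six-month horizon, or say that none is available.
- Calibrate the limit for repeated looks, and tabulate the stopping probabilities under no effect, benefit and harm.

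A simple single-look binomial limit will not do. With 25 treated per donor type, a false-stop rate of at most 5% would give 14 cases for DCD (null 36%, 0.033) and 10 for DBD (null 21.8%, 0.031). Power would be only 0.35 at a true DCD rate of 50% and 0.37 at a true DBD rate of 35%, and repeated looks would raise the false-stop rate. The figure of 25 is itself unsettled, because group C is cancelled (4.7, 8.2) and its livers are not reallocated. These limits should not be adopted as they stand.

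The cost is a paragraph and a small table, plus the calibration. The downside is that more background strictures are tolerated before a stop, which must be justified to the ethics committee.

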5.9 Ancillary / sub studies

5.9.1 Liver biopsies

Biopsies (20mm core biopsies) will be taken pre-perfusion, at the end of perfusion, and one hour after reperfusion in the recipient. They will be divided into two, with half in formalin for histological examination, and half in RNA later for transcriptomic studies. The histological examination will be done using haematoxylin and Eosin (H&E) stained sections and Martius Scarlet Blue (MSB) stained sections.

5.9.2 Bile duct

The end of the bile duct is usually trimmed to remove the crushed area where the cannula draining bile on the machine was tied. This end of bile duct will also be stained with H&E and MSB.

5.9.3 Perfusate samples

Perfusate samples will be taken before perfusion begins, at 30, 60, 90, 120, 180 and 240 minutes. 10mls will be taken and spun down and the cell free perfusate frozen for later analysis including assays of fibrin breakdown and markers of reperfusion injury.

6 Eligibility

6.1 Inclusion Criteria

A recipient of a liver from a deceased donor

6.2 Exclusion Criteria

- Inability to give informed consent
- Age <18 years
- Allergy to Latex or gentamicin by donor or recipient
- Hypersensitivity to TPA by donor or recipient

8.1 Liver perfusate

The OrganOx perfusate will be the same as routinely used in the centre, and will comprise 3 units of packed red cells, a plasma substitute (human albumin in Cambridge, Gelofusine at the Royal Free) together with the standard additives and infusions.

8.2 Trial material / source of drugs / presentation of drugs

Alteplase will be reconstituted with sterile water: 10mls for 10mg dose; 20mls for 20mg dose, and 50mls for the 50mg dose, to make a 1mg/ml solution. It should be drawn up into a 50ml syringe to which Normal saline will be added (10mg and 20mg doses only) to achieve a final volume of 50mls. The syringe containing alteplase will be placed on a syringe driver and connected to a three-way tap attached to the arterial cannula within the liver container for the first 3 groups, and on the portal reservoir for the 4th group. The site of infusion for the 5th group will be determined from a D-dimer analysis after completion of the first 4 groups.

One unit of fresh frozen plasma (approx. 250mls) will be run through a giving set or divided into five 50mls syringes; 50mls will be added to the soft shell reservoir, the remaining 200mls will be delivered over 60 mins using an infusion pump or syringe driver to the second port of the three-way tap.

Once the liver is placed on the circuit **and as perfusion is begun**, 20% of the total dose of alteplase for the study group (see below) is infused through the arterial cannula (groups A, B, and C) or portal reservoir (group D). The remainder of the dose delivered to the arterial cannula / portal reservoir infused over one hour.

Group	Alteplase bolus dose (mg)	Alteplase infusion dose (mg)	Infusion site
A	2	8	Hepatic artery cannula
B	4	16	Hepatic artery cannula
C	10	40	Hepatic artery cannula
D	2	8	Portal reservoir
E	10	0	To be decided

Addendum: The initial analysis of the 10mg dose data suggest this is more than adequate, so there will be no 50mg treatment arm (Group C).

It is important not to mix the FFP and alteplase before they are added by infusion since the plasminogen in FFP will be rapidly converted to plasmin, and this plasmin will itself be broken down rapidly afterwards.

8.3 Known drug reactions

Immune mediated hypersensitivity to alteplase is associated with sensitivity to gentamicin (traces may be present) and latex (rubber in the bung of the glass vial). Angio-oedema is also reported. It is unclear whether these will have any manifestation in an isolated perfused liver or the recipient of the same.

8.4 Legal status of the drug

Alteplase is licensed for thrombolytic treatment in acute myocardial infarction, thrombolytic treatment in acute massive pulmonary embolism with haemodynamic instability, and fibrinolytic treatment of acute ischaemic stroke.

8.5 Drug storage and supply

Once reconstituted, alteplase can be stored for 24 hours in a fridge at 2°C to 8°C, or 8 hours at 25°C. Once thawed, fresh frozen plasma can be stored for 24 hours at 4°C.

9 Study procedure and assessments

9.1 Informed consent

An information sheet will be sent to all recipients on the liver transplant waiting list who expressed a willingness to accept a deceased donor liver. Informed consent will be taken in hospital/clinic while on the waiting list although there may be occasions when the recipient is called in for a transplant having received the information letter but not been formally consented. They will be approached on the ward and given at least an hour to make a decision regarding participation.

9.2 Unconsented recipients

On rare occasions treatment of the liver according to the randomisation will begin with the consent of one patient, but a decision may be made to change recipient. Examples of such circumstances are as follows:

- The liver function during perfusion is such that the first recipient is not deemed appropriate, e.g., a suboptimal liver and a recipient likely to get a better liver soon on the National Liver Offering Scheme.
- The intended recipient is not able to receive the liver, for example, if he suffers an anaesthetic reaction before explant of the transplant and his operation must be abandoned
- A recipient of greater urgency requires the liver instead of the intended recipient. For example, when two livers are accepted, and the intended liver for the urgent case turns out to be unusable, such that the liver on the machine is required for the urgent case.

In such circumstances the actual recipient should be informed, before the transplant (unless they are unconscious or encephalopathic) that the liver has been part of a trial. They should then be asked if they wish to participate or not and shown the patient

information sheet prepared for this eventuality. If they decide not to participate, no further trial intervention (e.g. taking biopsies for RNA analysis) will be undertaken.

9.3 Recipient who cannot consent

It is the intention to only enrol consenting subjects into this trial. However, in the circumstance above, where the liver has commenced perfusion and the trial treatment has begun, and is then switched from an intended recipient who has consented to an urgent patient who is unable to consent (e.g. he is unconscious or encephalopathic), and in the absence of the next of kin, a clinician independent from the study team will be required to give their approval. This could be a consultant hepatologist, consultant surgeon, or the medical director. They should record their agreement in the patient's notes. In this setting the transplant will proceed as "normal care" and no research samples will be taken, no research biopsies taken, and no research data recorded. In this circumstance, the patient may be approached once he has recovered and retrospective consent sought for data collection.

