5.8 Criteria for Discontinuation

5.8.1 *Individual liver*

5.8.1.1 *Transplant criteria*

Criteria favouring transplantation of liver include:

Perfusate:

- ALT < 6000 u/L

- Lactate fall to <2 in 2 hours
- Glucose falling hour on hour after 2 hours
- Producing bile
- Need for <40mls 8.4% NaHCO₃ in the first 4 hours to maintain a perfusate pH>7.2 as measured on near patient blood gas machine (not the Organox *metra* reading)

Bile

- pH>7.6
- Bile glucose <2.0mmol/L or >10mmol/L less than perfusate.

Criteria favouring non-use of liver include

Perfusate

- ALT>10000iu/L
- Lactate>2.5 at 2 hours
- Glucose failing to fall after the second hour
- Not producing bile
- Requirement for >60mls 8.4% NaHCO₃ in first 4 hours of perfusion

Bile

- pH<7.5
- Bile glucose >2.0mmol/L or <10mmol/L less than perfusate

The above criteria reveal an area of uncertainty with livers between the definitely usable and definitely unusable. There are currently no internationally accepted viability criteria, but those proposed by ourselves are in accord with most other criteria, and are based on the largest published experience to date^{14,15}. That said, a recent case, and the reason for amendment 5, has suggested that assessment at 2 or 4 hours may be too soon and a longer period of perfusion may be advisable in some livers to distinguish between a liver that will not recover, and one that is stunned and recovers after 4 hours.

5.8.1.2 *Livers outside criteria with late recovery of function*

Where the criteria are outside those favouring transplantation, but the liver appears to recover function as perfusion continues, a decision to use the liver will be taken in consultation with a member of the transplant team who is not involved in the research (typically both the on call hepatologist and surgeon), and the appropriateness of the proposed recipient will also be reviewed. It may be necessary to change recipient if there remains doubt over the liver

5.8.1.3 *Change of recipient after liver treatment has begun*

Any decision to change recipient will need to go through the national liver offering protocol, that is, it will need to be offered back to all other centres as a “Fast Track” offer and only if they decline its use can it be reallocated locally (unless it was originally accepted as a Fast Track with no named recipient when there is no need to offer the liver back).

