16.1 Consent

All patients will freely give their informed consent to participate in the study. A patient may decide to withdraw from the study at any time without prejudice to their future care.

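### Section 9.3 makes entry into the data depend on recovery for a recipient of a treated, reallocated liver who could not consent, so deaths before recovery drop out while survivors can be added

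*Protocol*

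**What the plan says.** Protocol 9.2 covers a change of recipient after treatment has started: "On rare occasions treatment of the liver according to the randomisation will begin with the consent of one patient", and the liver may then go to someone else. Recipients with capacity are told before the transplant and asked whether they will take part.

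Protocol 9.3 covers the narrower case of an urgent recipient who is unconscious or encephalopathic. There, "in the absence of the next of kin, a clinician independent from the study team will be required to give their approval". The transplant goes ahead as ordinary care, and "no research samples will be taken, no research biopsies taken, and no research data recorded". The section then gives the one later route into the data: "In this circumstance, the patient may be approached once he has recovered and retrospective consent sought for data collection".

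Other sections that bear on this:
- 4.9.1 makes safety, including excess bleeding in recipients, the primary objective. 5.6 lists post-reperfusion blood loss as a primary endpoint and return to theatre for bleeding within 24 hours as a secondary one.
- 5.8.3 ends recruitment on a count of livers transplanted, 30 DBD and 30 DCD.
- Section 7 randomises one transplanted liver in six to FFP without TPA.
- 10.6 adds a comparison with matched historical recipients.
- 11.3 lists peri-operative death and haemorrhage needing re-operation among expected events that are not to be reported as AEs or SUSARs.

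**The concern.** A rule that admits a recipient to the dataset only after recovery selects on outcome. The missing recipients would be those who died or stayed incapacitated, so the missingness is informative and its direction is known: observed mortality, and any bleeding that led to death, would look lower than it was. Because 10.4.5 measures survival from the date of transplant, a recipient added later also brings in a stretch of time in which he could not have died and still been counted.

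This falls on the main question of a small safety pilot. The two bleeding endpoints arise in the operation or within a day of it, before any recovery. Routine safety reporting does not clearly fill the gap, given 11.3. The protocol has no trial committees (2.6) and considers external supervision unnecessary (10.7), so no outside body is placed to notice a missing case. A liver of this kind may also count toward the 60 under 5.8.3 while its recipient's outcome is absent.

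**Working it through.** **Plan's own figures.** The protocol gives no number of reallocated livers and no death risk for urgent recipients, so there is no figure on this point to reproduce. Its perfusion numbers do reproduce (30/(1 − 1/3) = 45.0 DCD; 30/(1 − 0.15) = 35.3 DBD, stated as about 35), but they play no part below.

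**Who can enter the data after reallocation, read from 9.2 and 9.3**

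| Recipient of a treated liver | Route into the data | Settled before the outcome is known? |
|---|---|---|
| Has capacity, asked before transplant | Agrees or declines | Yes |
| Cannot consent, later recovers | Retrospective consent | No |
| Cannot consent, bleeds or is retransplanted, then recovers | Retrospective consent | No |
| Cannot consent, dies or never regains capacity | None described | Excluded by the outcome |

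The last row is the defect.

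**Number of TPA recipients.** 60 transplants with one in six FFP-only: 60 × 5/6 = 50 TPA and 10 controls, approximately.

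**Deaths expected among 50**, at the 1 to 2% peri-operative rate in 11.3:
- 50 × 0.01 = 0.5 and 50 × 0.02 = 1.0.
- P(at least one) = 1 − 0.99^50 = 39% and 1 − 0.98^50 = 64%.

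The whole peri-operative mortality signal may thus be zero or one death.

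**Effect if one death goes unrecorded** (Clopper-Pearson; lower limit = Beta quantile 0.025 with parameters x, n − x + 1, or 0 when x = 0; upper limit = Beta quantile 0.975 with parameters x + 1, n − x):
- All counted: 1/50 = 2.0%, 95% CI 0.05 to 10.6%.
- That recipient absent: 0/49 = 0%, 95% CI 0 to 7.3%.

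This is conditional: it supposes that the death falls on a recipient covered by 9.3.

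**Unconditional size, by assumption.** Let k be the number of TPA recipients under 9.3 and q their risk of death before recovery. Expected lost deaths = kq; P(at least one lost) = 1 − (1 − q)^k.

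| k | q | Expected lost deaths | P(at least one lost) |
|---|---|---|---|
| 1 | 2% | 0.02 | 2% |
| 2 | 10% | 0.20 | 19% |
| 3 | 20% | 0.60 | 49% |
| 5 | 30% | 1.50 | 83% |

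With k of 1 or 2 and the protocol's own 1 to 2%, the expected loss is only 0.01 to 0.04 deaths. With k = 3, q = 20% and the other 47 at 2%, the true rate is (47 × 0.02 + 3 × 0.20)/50 = 1.54/50 = 3.1%, and the expected observed rate is about 0.94/49.4 = 1.9%.

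**The case against.** The strongest reply is that the affected group is narrow and the restriction is an ethical one. Section 9.3 applies to an urgent recipient without capacity, and its clinician-approval route is worded for absent next of kin; it does not say what happens to the data when kin are present. Sections 2.7.5 and 2.7.6 show that a provision for retrospective consent did not receive a favourable opinion as submitted and was revised with separate consent forms. FFP-only livers pass through the same filter, so the randomised comparison is treated alike in both arms. All of this stands, and it limits the size. It does not remove the dependence on recovery: the absolute event rate after TPA is still affected, and an excess of early deaths on TPA is what the filter would hide.

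A reader might infer more than the protocol supports:

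- *That 9.3 contradicts the eligibility rules.* Section 6.2 excludes "Inability to give informed consent" and 16.1 says "All patients will freely give their informed consent to participate in the study". But 9.3 is framed as a deliberate exception: the recipient is not enrolled at transplant, and anyone added later has capacity and consents.
- *That every bad outcome is lost.* A recipient who bleeds, returns to theatre or loses the graft and then recovers can still be counted. Only death or lasting incapacity before the approach removes him, and a death after retrospective consent can be counted.
- *That all reallocated livers are affected.* One example in 9.2 is "The liver function during perfusion is such that the first recipient is not deemed appropriate". Such recipients, unless unconscious or encephalopathic, are asked before transplant, so their entry does not depend on outcome.
- *That outcomes at other centres are lost.* Section 5.8.1.3 says of a liver whose recipient changes that "it will need to be offered back to all other centres as a “Fast Track” offer" (with an exception for livers first accepted that way). It describes allocation and is silent on data collection. Non-capture there is an inference.
- *That a fixed share of bleeding events disappears.* At 10% in 11.3, about 5 re-operations for haemorrhage are expected in 50. Subtracting one assumes that the event falls on one of these few recipients and is fatal; survivors of re-operation remain recoverable.

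A fatal bleed judged a suspected unexpected reaction could be reported under 11.6. That would be a safety report, not an entry in the comparison, and the listing in 11.3 makes it less likely.

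**Conclusion.** The point holds in a limited form. For recipients who could not consent at transplant, 9.3 makes inclusion depend on surviving with capacity, and no other section gives a route for those who do not. The direction is toward apparent safety. With five livers in six allocated to TPA, most such cases would be TPA-exposed, and the historical comparators in 10.6 have no stated filter of this kind.

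The expected effect is small, because reallocation is described as rare: 0.01 to 0.04 lost deaths if one or two TPA recipients are affected at the protocol's own rates. It rises to 1.5 only with five such recipients at a 30% risk. Both the counts and the higher risks are assumptions. What makes the rule worth correcting is that a single case decides the headline: one observed death in 50, or none in 49.

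**What to change.** Amend 9.3 and the analysis sections so that inclusion is settled by consent status at the time of transplant, before the outcome is known:

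1. Keep recipients who could not consent before transplant out of the main safety and efficacy comparisons.
2. Describe any retrospectively consented data separately, labelled as coming from survivors.
3. Report, by allocated arm, the number of treated and transplanted livers whose recipient contributed no data, with the reason.
4. State whether such livers count toward the 30 DBD and 30 DCD transplants in 5.8.3.

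The cost is a short amendment, one table, and the loss of a few survivors' data from the main comparison. This does not recover the missing deaths, and the main results would then describe recipients who could consent before transplant. It removes selection on outcome and makes the number missing visible.

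Collecting a minimal safety outcome for every such recipient would be better, because the deaths would then be counted. It depends on REC agreement, which the history in 2.7.5 shows cannot be assumed, so the four steps above should not wait for it.
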